2.2.2 Secondary Outcomes

- Parental report of provider-diagnosed AD - This parental report of AD question has been validated previously by our group and was found to have adequate sensitivity and specificity during our trial planning activities.³⁹

- AD as diagnosed by the Children's Eczema Questionnaire (CEQ) – The CEQ is a newly developed 2-question parental questionnaire based on the U.K. Working Party criteria.⁴⁰ This instrument will be used to capture dyads not evaluated by their provider or lost to follow-up (Appendix A).
- Parental report of sleep loss of the infant reported as average parental report of days per week of disrupted sleep in their infant (1 week recall) measured at 12 and 24 months.
- Any prescription topical medication use or over-the-counter hydrocortisone usage recorded by parent or recorded from records review by research coordinator at 24 months.
- Asthma risk questions from the modified Asthma Predictive Index (mAPI) that uses family history, atopic dermatitis, sensitization history, and wheezing episodes to predict the development of asthma measured by parental report.⁴¹ This will be recorded as either high risk or low-risk at 12 and 24 months following mAPI criteria (Appendix B). Wheezing episodes will be assessed using the International Study of Asthma and Allergies in Childhood (ISAAC) questionnaire.
- Parental report of immediate food allergy symptoms – A general question regarding the development of red rash/hives, lip swelling, wheezing, abdominal pain, or vomiting that developed in the infant within two hours of eating a food.
- Parental report of a provider diagnosis of food allergy that was confirmed by prick testing or IgE blood test.
- One question global health status from the PROMIS Pediatric Global Health (PGH-7) instrument.⁴² (Appendix C)
- In infants who develop AD, a logic model in our survey instrument will ask the following parental reported outcomes in the 12- and 24-month questionnaires:
 1. Time to onset of AD as measured by parental report of eczema age of onset.
 2. Time to onset of AD as measured by provider-recorded date of first diagnosis retrieved from record review of chart by research coordinator.
 3. AD symptom severity as reported by the Patient-Oriented Eczema Measure (POEM) instrument⁴³ (Appendix D).
 4. Parent-reported global severity of eczema assessment – mild, moderate, severe

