10.4.3 Secondary analyses of primary endpoint

As a sensitivity analysis, we will perform a complete-case analysis using only subjects who have non-missing outcome data in a logistic regression model adjusting for stratification variables as well as covariates that we find to be associated with missing AD status.⁷⁸ The effect of emollient use will be evaluated with a model similar to the primary analysis, but substituting an indicator of regular reported emollient use (≥ 3 days per week) for intervention allocation. In a separate model, we will include a variable for bathing frequency. In the likely case that bathing and emollient use frequency are associated, we will create and test a combined categorical variable. We will return to the primary intervention-effect model and consider additional covariates previously found or suspected to be associated with AD, such as climate, season of birth, pet ownership, bathing frequency, and characteristics of the living environment using a change-in-estimate approach.⁸³ Finally, we will compare clinic-stratified intervention effects on the primary AD outcome and test their equality with a Breslow-Day test; the purpose is to identify 'large' differences where further investigation into potential protocol deviations or other factors may be warranted, and these results will be interpreted with caution.

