5.1. Statistical Hypotheses and Outcome Definitions

1. Our primary hypothesis is that the intervention will result in significantly **lower cumulative incidence of provider-diagnosed AD by age 24 months**.

After two years of follow-up, we will calculate the proportions of children diagnosed with AD by trained primary care providers in the intervention and control arms. Clinicians will be trained in pediatric AD standard diagnosis criteria.⁴ As our primary analysis, we will test the hypothesis that the ratio of the intervention:control proportions, a relative risk (RR) measure, is significantly smaller than 1 with a two-sided test: **RR ≠ 1 vs RR= 1**. This analysis will be conducted in an intention-to-treat (ITT) analysis dataset of all randomized participants with multiple imputation for missing outcomes.

Provider-diagnosed AD, the current gold standard, will be recorded during chart abstraction and referred to as **GS-AD**. The case report form (CRF) includes a question:

Was there a diagnosis of AD (includes eczema, atopic eczema, atopic dermatitis, and neurodermatitis)? with forced choice responses:

- 1, Yes
- 0, No / No documentation
- 2, Not sure / Possible - AD diagnosis is not confirmed

The CRF further elaborates:

To check "Yes", there must be an official diagnosis from a provider. If a provider is considering eczema as a possibility, or if a parent thinks the child has eczema, mark "Not Sure/Possible" and provide verbatim description from the medical record. Choose "Not sure/Possible" if there is some evidence of eczema but no official diagnosis.

All "not sure/possible" records and their explanatory notes will be reviewed by the principal investigator or dermatology physician co-investigators under blinding before the dataset is locked for analysis. Fields describing the presence and date of onset of similar or comorbid conditions-- such as candida of the skin, impetigo, and molluscum--are part of this record. Parent responses to the Childhood Eczema Questionnaire^{5,6} (CEQ) (see item 2c below) will also be available for review during this determination.

After this review, any child with a "Yes" response or adjudicated as probable AD by physician reviewers will be considered to have AD and the outcome variable will be set to equal 1. "No" and "Not sure" responses adjudicated as not probable AD will be considered not AD and the outcome will be set to 0.

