We will test additional secondary hypotheses comparing the intervention arm to controls with two-sided inference tests. In all of the items below, "I don't know" responses will be treated as missing:

2. Lower cumulative incidence of AD at 24 months by alternative diagnosis definitions, namely:
 - a) **Parent report (PR-AD)** of provider diagnosis⁷, as a yes response to the following at any time during follow-up:

Over the past 12 months, has a healthcare provider said your child has eczema or atopic dermatitis?
 - b) **Diagnosis by the UK Working Party criteria⁸ (UK-AD)** at any time during follow-up, defined as a yes response to dry skin and a rash that causes itching, i.e.:

Does your child have, or has your child had, a red rash or eczema which can come and go?

Has this red rash or eczema ever caused any itching, scratching, or rubbing? (Note: Even a small amount counts)

Along with responses as follows (note that responses can be given at different data collection time points):

- [at least one selected] Select all of the areas where the red rash or eczema has been in the past year:
 - Cheeks
 - Around the eyes, ears, scalp, forehead, or neck
 - Folds (creases) of elbows or behind the knees
 - Wrist or ankle
 - Outer arms/ legs
 - Trunk
- [at least one yes] Has at least one of your baby's blood-related PARENTS, BROTHERS OR SISTERS ever been diagnosed with asthma, or hay fever (seasonal allergies)?
 - Has your child ever been diagnosed with asthma by a healthcare provider?
 - Has your child ever been diagnosed with hay fever or springtime allergies by a healthcare provider?
 - Has your child ever been diagnosed with a food allergy by a health care provider?
- [Yes] Does your child have dry skin?

Note that the published version includes food allergy in first degree relative, which is not collected in this study.

c) Diagnosis by validated multi-item **Childhood Eczema Questionnaire (CEQ-AD)** completed by parent^{5,6}, if yes responses to all of the following three questions at any time during follow-up:

Does your child have, or has your child had, a red rash or eczema which can come and go?

Has this red rash or eczema ever caused any itching, scratching, or rubbing? (Note: Even a small amount counts)

Has this red rash/eczema affected any of the following areas during the last week: around the eyes, ears, scalp, cheeks, forehead, neck, trunk, folds of the elbows/behind the knees, wrist or ankle, outer arms/legs?

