5.4. Analysis of the Secondary Endpoints

Definitions of secondary endpoints are in section 5.1

The following **binary outcomes** will be evaluated with log-binomial models similar to Equation 1 for the primary outcome. When comparing intervention versus controls, we will use a Wald test for the intervention regression coefficient at the 0.05 level of significance.

2. As secondary/sensitivity analyses, we will test the intervention effect with alternative definitions of AD at 24 months, namely:
 - a) Complete case analysis of the primary endpoint (GS-AD), provider diagnosis, adjusting for stratification variables as well as covariates that we find to be associated with missing AD status;
 - b) PR-AD- Parent report of a provider diagnosis at any point in the ITT dataset;
 - c) UK Working Party in the ITT dataset;
 - d) CEQ-AD- Children's Eczema Questionnaire (CEQ) in the ITT dataset;

3. Cumulative incidence of AD at 18 months.

In addition to the binary models, we will conduct a multivariate or latent variable analysis to estimate cumulative incidence in each treatment arm using multiple candidate definitions and estimating the correlations between the definitions.

4. Cumulative incidence of AD treated with prescription and/or over-the-counter medication(s)

- a) Clinically-significant severe AD (CS1-AD)
- b) Clinically-significant moderate to severe AD (CS2-AD)

Non-AD (but still binary) outcomes include the following:

5. Probable or predicted asthma by the modified Asthma Predictive Index, and/or symptoms of asthma such as wheezing or prescribed bronchodilator.

6. Food allergy, defined by:

- a) Parental report of provider diagnosis of food allergy
- b) Positive prick testing or IgE blood test
- c) Parental report of immediate food allergy symptoms
- d) Near definite FA- provider diagnosis, positive test, and immediate symptoms

7. Prescription topical medication use or over-the-counter hydrocortisone use in (1) the ITT dataset, and (2) the AD dataset

- a) reported by parent
- b) identified during chart review

For **continuous** outcomes, use histograms and normal quantile plots to check for obvious lack of symmetry. Test for group differences with a linear regression model similar to the log-binomial models described above, using bootstrapped standard errors if the distribution of responses is non-normal.

8. In the AD dataset, severity of symptoms as measured by:

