If $>5\%$ of observations are missing outcomes, then further steps are needed. In addition to the analytic steps described here, we will discuss with members of the study team who interact with participants and clinic staff and may have insight into reasons for loss to follow-up that may or may not be reflected in recorded data. As a first step, we will create an indicator variable $R=1$ if the outcome is missing, $R=0$ if not missing. This variable R can be used to test whether missingness is associated with other variables, particularly:

- Study arm
- Family history of atopy
- Date of enrollment in study
- Parent report of AD
- Child's Eczema Questionnaire (CEQ) signs of AD
- UK Working Party criteria for AD
- PBRN

If differences are found (at $p < 0.10$, approximately, for an inclusive approach) then covariate-dependent missingness at least partly explains the missingness mechanism. Any such variable should be used in the multiple imputation model (or included in the main model without imputation) to produce unbiased estimates.

Multiple imputation will be performed using iterative chained equations over five (5) imputation sets. At the time of writing, the performance of multiple imputation when the model includes a random effect, such as the recruiting clinic in our model, is not well understood, and software to run the model we have proposed under multiple imputation is not readily available. (The estimation command is not available in Stata version 16, for example). Alternatives include (a) substituting a Poisson or logistic model, (b) omitting clinic, which should not be strongly associated with treatment outcome, or (c) Bayesian approaches, which could be especially useful if we suspect that data are missing not at random. The multiple imputation results will be considered the primary findings and will be reported along with complete case analysis.

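### The complete-case RR model in SAP 5.4 item 2a can adjust for follow-up measures of AD itself, which would pull a real effect towards 1

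*SAP*

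**What the plan says.** - **SAP 5.4 item 2a** repeats the primary endpoint in complete cases, using a log-binomial model like Equation 1, "adjusting for stratification variables as well as covariates that we find to be associated with missing AD status". **Protocol 10.4.3** has the same rule in a logistic model: "covariates that we find to be associated with missing AD status". Neither limits the covariates to baseline.
- **SAP 5.9** gives the only list of variables to test against a missing outcome, applied at about p<0.10 when more than 5% of outcomes are missing. It includes "Parent report of AD", CEQ signs of AD and the UK Working Party criteria. It then says: "Any such variable should be used in the multiple imputation model (or included in the main model without imputation) to produce unbiased estimates".
- **SAP 5.1 item 2** presents these three as alternative definitions of AD at 24 months, built from parents' answers given during follow-up; parent report is scored "as a yes response to the following at any time during follow-up".
- CEQ lies closest to the primary outcome. Its answers "will also be available for review during this determination" when physicians adjudicate unsure charts (SAP 5.1), and protocol 2.2.2 says of it: "This instrument will be used to capture dyads not evaluated by their provider or lost to follow-up".
- On reporting, SAP 5.9 says: "The multiple imputation results will be considered the primary findings and will be reported along with complete case analysis".

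**The concern.** Adjusting for a baseline predictor of missingness is sound. Adjusting for a second, error-prone reading of the outcome, taken after randomisation, is not. If the intervention prevents AD it also lowers parent-reported AD, so conditioning on parent report removes part of the effect being estimated.

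Selection is plausible because of how SAP 5.9 defines missingness. A child with AD already in the chart is never missing, so the missing group tends to hold fewer children with AD, and any measure of AD tends to be associated with missingness.

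The complete-case RR is printed beside the imputed one as a check on it. An estimate pulled towards 1 could make a sound primary result look fragile.

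**Working it through.** **1. The plan's own figure.** Inputs from SAP 2.3: control risk 0.24, intervention risk 0.168 (RR 0.70), two-sided 0.05, 80% power. With mean risk 0.204, n per arm = [1.960·√(2·0.204·0.796) + 0.8416·√(0.24·0.76 + 0.168·0.832)]² / 0.072² = (1.117 + 0.478)² / 0.005184 ≈ 491. The total of 982 reproduces.

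**2. Why the RR moves and the odds ratio does not.** Take 1,000 children per arm, no missing outcomes, and a proxy with assumed sensitivity 0.8 and specificity 0.95 in both arms.

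| | Control AD/total | Intervention AD/total | RR | OR |
|---|---|---|---|---|
| Proxy positive | 192/230 = 0.835 | 134.4/176 = 0.764 | 0.915 | 0.639 |
| Proxy negative | 48/770 = 0.062 | 33.6/824 = 0.041 | 0.654 | 0.639 |
| All | 240/1000 | 168/1000 | 0.700 | 0.639 |

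The Mantel-Haenszel RR across the two strata is (134.4·230/406 + 33.6·770/1594) / (192·176/406 + 48·824/1594) = 0.855. A Poisson fit on arm and proxy gives 0.854 and the SAP's log-binomial model 0.898. The odds ratio is 0.639 in both strata and overall.

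**3. Large-sample fits with missing outcomes.** Assumed: family history in 50%; control risk 16% or 32% by family history (mean 24%); 20% of children lost; a share of the lost children's AD already charted, from 0 to 1. The outcome is missing if the child is lost and has no charted AD, so 0.20 × (1 − share × 0.204), or 16% to 20%, of outcomes are missing. Poisson model on arm and family history, true RR 0.70:

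| Sensitivity/specificity | RR without proxy | RR with proxy |
|---|---|---|
| 0.6/0.9 | 0.700–0.713 | 0.766–0.780 |
| 0.7/0.9 | 0.700–0.713 | 0.791–0.805 |
| 0.8/0.95 | 0.700–0.713 | 0.856–0.867 |
| 0.9/0.97 | 0.700–0.713 | 0.913–0.921 |

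At a true RR of 0.90 (half charted), 0.903 becomes 0.928 to 0.976. At a true RR of 1.00 with equal accuracy, the fitted RR is 1.000 in all 20 combinations.

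**4. Protocol 10.4.3, logistic model, same cells.** The arm odds ratio is 0.631 without the proxy and 0.632–0.634 with it. The RR from average predicted risks moves from 0.700–0.713 to 0.77–0.92. Simulated power (600 trials, half charted) falls from 87% to 76% at 0.6/0.9 and from 88% to 49% at 0.8/0.95.

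**5. The rule as written: proxy enters only if selected at p<0.10.** N=1,250, true RR 0.70, robust Poisson, 2,000 simulated trials per case. Ranges run over the four accuracy pairs.

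| Share of lost children's AD already charted | Chance of selection | Mean RR | Power |
|---|---|---|---|
| None | 10–11% | 0.71–0.72 | 77–81% |
| Quarter | 23–48% | 0.71–0.80 | 57–80% |
| Half | 60–96% | 0.75–0.91 | 31–77% |
| Three quarters | 93–100% | 0.77–0.92 | 29–74% |
| All | over 99% | 0.78–0.92 | 31–76% |

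Without the proxy, power is 82–89%. If only 40% of children with a missing outcome have survey data (1,500 trials per case), selection falls to 9–11%, 16–29%, 32–72%, 62–98% and 88–100%, and mean RR to 0.70–0.72, 0.71–0.76, 0.73–0.85, 0.75–0.91 and 0.77–0.92.

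**6. Unequal accuracy, illustration only.** Parents are unblinded (protocol 4.5). At a true RR of 1.00, sensitivity 0.8, control specificity 0.90, half charted and the proxy in the model, intervention specificity of 0.88 or 0.92 gives RR 0.97 or 1.04. The documents do not indicate any such gap.

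**The case against.** The strongest reply is that nobody intends this. SAP 5.9 does not mention item 2a. The three measures are themselves the outcomes of items 2b to 2d, directly below it. Protocol 10.4.1 places parent-reported diagnosis in the imputation model, SAP 4.3 says the missingness findings inform imputation, and protocol 13.3 speaks of key covariates collected at baseline. That shows the likely intent. It does not exclude the three measures, and SAP 5.9 expressly offers the main model as a place for any selected variable. The SAP 5.3 statement that no other baseline characteristics enter governs the primary model, not item 2a.

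It is also fair that the size rests on assumed accuracy, charted share and survey response, and that the trial simulations used robust Poisson, a fallback in SAP 5.3, rather than log-binomial. In the simpler fits without family history or missing outcomes (assumed sensitivity 0.5–0.9, specificity 0.85–0.95), log-binomial moved further: 0.77–0.92 against 0.74–0.89 for Poisson. Children without survey answers would also drop out of a model containing the proxy; that was not modelled.

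Two stronger readings should be resisted. A reader might infer that the protocol's logistic version attenuates the arm odds ratio too; with equal accuracy it is essentially unchanged (step 4). A reader might also infer that SAP 5.9 presents the complete-case figure as the unbiased one. It does not: its claim of unbiased estimates covers both imputation and main-model use, and it makes the imputed results primary. The error is only that the claim fails for main-model use of these three measures.

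**Conclusion.** The point holds as a conditional defect in the wording. The rule admits follow-up measures of AD into the complete-case RR model. If one enters and the effect is real, a true RR of 0.70 appears as about 0.77 to 0.92 under the assumed accuracies. Averaged over selection, the distortion is negligible if little AD was charted before loss, because the proxy is then rarely selected. It can be large if half or more was charted.

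The documents do not support reading this as a source of false positives: with no true effect and equal accuracy there is no bias, and the 5% test rejected in 4–6% of simulated trials. Nor does it undermine the primary analysis, which is affected only through the main-model option in SAP 5.9. The raw RR (SAP 5.3) and the best-case, worst-case and tipping-point analyses (SAP 5.10) would help to expose a discrepant complete-case result, though not explain it. It should be fixed because the correction is specific and free, not because the trial's conclusion depends on it.

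**What to change.** - **SAP 5.4 item 2a and protocol 10.4.3:** limit complete-case covariates to the stratification variables and other baseline variables associated with missingness, for example enrolment date and PBRN.
- **SAP 5.9:** limit the parenthesis that allows selected variables in the main model to baseline variables.
- **SAP 5.9:** state that parent-reported AD, CEQ and UK Working Party status serve only as auxiliary variables in the imputation model, as protocol 10.4.1 already does for parent-reported diagnosis.

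The cost is a few words in two SAP sections and one protocol sentence. No new data are needed and the primary estimand does not change.

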2.3. Sample Size and Recruitment Duration

1,250 parent/infant dyads (625 per arm) will be enrolled from 25 community-based family medicine and pediatric practices in four states (Oregon, Colorado, Wisconsin, and North Carolina). All parents/legal guardians, including males and females 18 years of age and older who meet inclusion/exclusion criteria are eligible for study participation. Recruitment is expected to take place over the course of 31 months; the time from start of recruitment until final two-year follow-up on all subjects is five years.

Power for Aim 1. For the purpose of the primary analysis, we include a sufficient number of babies in a 1:1 ratio for the two study arms to provide an overall type I error rate of 0.05 and 80% power to detect a 30% relative reduction in cumulative incidence of AD by two years of age (RR=0.7). In our planning grant, we determined the baseline cumulative incidence of AD in this age group and target clinics at 24%, which is consistent with recent population-based 2-year prevalence in the U.K.¹. Because our trials in high-risk populations of daily vs no emollient have shown reductions of 50%, we assume a more conservative 30% reduction to 16.8%. Using a test of two proportions, a total of 982 babies (491 per arm) are required to detect this difference. Allowing for an approximate 20%

¹ The screening questionnaire includes the question "Has at least one of your baby's blood-related PARENTS, BROTHERS OR SISTERS ever been diagnosed with asthma, eczema (atopic dermatitis) or hay fever (seasonal allergies)?" Strata are split at "Yes" responses vs. "No, or don't know."

loss to follow-up, we plan to enroll 1,250 babies (625 per arm). Sample size calculations were performed using Stata/IC version 16.1.

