3.1. Level of Statistical Significance

In the primary analysis, use a type I error rate of 0.05. Secondary outcomes will be considered significant at $\alpha=0.05$ and exploratory analyses at $\alpha=0.1$. All tests will be two-tailed.

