- Peripheral eosinophilia ($\geq 4\%$), from chart review

7. Lower prevalence of food allergy, measured as

- a) the proportion with parental report of provider diagnosis, defined as a "yes" response to this question derived from the National Health Interview Survey¹⁰:

Has your child ever been diagnosed with a food allergy by a health care provider?

- b) Parental report of a provider diagnosis of food allergy that was confirmed by prick testing or IgE blood test, defined as "yes" to both the previous question and this one:

Did your child have a positive test to any of the above foods using a skin prick test or blood test?

- c) Parental report of immediate food allergy symptoms: a "yes" response to

Has your child ever had an allergic reaction within 2 hours of eating a food? (i.e. swelling of the face or lips, red rash, hives, stomach pain, vomiting, or wheezing/difficulty breathing)?

d) All three (3) of the above criteria, which may be described as near definite food allergy.

8. Lower prescription (Y/N) topical medication use or over-the-counter hydrocortisone usage in (1) all children and (2) those with AD only.

a) Parent reported prescription topical medications, defined as either or both of the following responses to this question:

Have you treated the red rash or eczema with any of the following? (check all that apply)

Prescription steroid/cortisone cream/ointment from a healthcare provider (example, hydrocortisone 2.5% or triamcinolone cream or ointment)

Prescription non-steroidal cream/ointment (example: Protopic, tacrolimus, Elidel, Eucrisa)

b) Parent-reported prescription or over-the-counter topical medications, defined as the prescriptions above *or*:

Hydrocortisone cream that you can buy without a prescription

Other anti-itch cream that you can buy without a prescription

c) Therapy(ies) recorded in chart; see definition for CS-2 above for description of prescription and over-the-counter therapies.

9. Lower severity of AD symptoms in intervention vs control *cases* as reflected by

a) Lower mean Patient-Oriented Eczema Measure (POEM), a validated symptom index that includes sleep and itch¹¹. Each of the questions has the possible responses of (0, No days | 1, 1-2 days | 2, 3-4 days | 3, 5-6 days | 4, Every day). To score, calculate the sum of the seven items for any respondent who answered at least five of the component questions (if the incomplete responses are <10% of the total responses).

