- a) Mean Patient-Oriented Eczema Measure (POEM) (a) averaged and (b) summed across all items in the ITT dataset.
- b) Mean score on the 30-point Infants' Dermatitis Quality of Life Index (IDQOL) summed across items in the ITT dataset

Age at onset will be tested using either pooled logistic regression or time-to-event methods for interval-censored data. For these analyses, age of onset will be indexed to the quarterly contact when the parent reported a diagnosis or to the closest corresponding age if the first diagnosis date is in the child's medical chart. Although we may not have sufficient sample size to detect an age-dependent treatment effect, it is possible that the greatest protective effects will be observed at early ages. Kaplan-Meier curves or similar visualizations may help to evaluate differences in treatment effect by age of onset.

9. Age of onset to the nearest 3 months determined by

- a) parental report of eczema from quarterly contacts or annual questionnaires
- b) provider-recorded date of first diagnosis retrieved from record review of chart by research coordinator indexed to the nearest quarter of follow-up

Mean days of disrupted sleep will be treated as a **count** variable and tested with a Poisson model similar to those described above.

10. Lower mean days of disrupted sleep in the past week for infants reported by parents at
 - a) 12 months
 - b) 24 months

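### POEM and IDQOL are tested between arms only among children who developed AD, so the difference is not a treatment effect, and SAP 5.4 item 8 names two datasets for the same test

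*SAP*

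**What the plan says.** SAP 5.1 item 9 states the hypothesis as "Lower severity of AD symptoms in intervention vs control" cases. SAP 5.4 item 8 begins "In the AD dataset, severity of symptoms as measured by", and SAP 3.6 defines the AD population as children with AD diagnosed on chart review. Table 4 lists POEM and IDQOL under that population.

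Sub-item 8a nevertheless has POEM "summed across all items in the ITT dataset", and 8b also refers IDQOL to the ITT dataset. The two labels are not interchangeable: item 7 of the same list uses them for two separate analyses.

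Protocol 2.2.2 and 10.2.2 and the schedule in SAP Table 3 collect POEM and IDQOL only in infants who develop AD. No score is assigned to the others.

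The test is a linear regression on arm, adjusted for the stratification variables (SAP 5.4; Protocol 10.4.4). SAP 3.1 declares secondary outcomes significant at 0.05, and adds "All tests will be two-tailed".

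**The concern.** Being in the AD population is an event after randomisation, and it is the event the trial hopes to make less frequent. If the intervention works, the intervention cases are those that were not prevented, and they are compared with all control cases, including those that emollient would have prevented. Randomisation does not protect that comparison. Family history and clinic in the model cannot restore it, because the selection depends on which cases were prevented. The sensitivity analyses in SAP 5.10 do not address it, and no caution on interpretation is given.

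A significant difference in either direction could therefore be reported as an effect on severity when no remaining child's disease had changed. The ITT wording in 8a and 8b does not avoid this, since it cannot be carried out without a score for children who have no AD.

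**Working it through.** **Inputs from the SAP.** Section 2.3 puts the "baseline cumulative incidence of AD in this age group and target clinics at 24"%, and adds "we assume a more conservative 30% reduction to 16.8"%. The design asks for "80% power to detect a 30% relative reduction in cumulative incidence of AD by two years of age (RR=0.7") at two-sided 0.05.

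**The plan's own figure.** With a pooled variance and p̄ = 0.204:

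n = [1.96 × √(2 × 0.204 × 0.796) + 0.842 × √(0.24 × 0.76 + 0.168 × 0.832)]² / 0.072² = 491 per arm, 982 in total. This agrees with SAP 2.3. The documents give no power or sample size for POEM or IDQOL.

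**Size of the comparison.** 1,250 enrolled less about 20% leaves 500 per arm. Expected cases are 500 × 0.24 = 120 and 500 × 0.168 = 84. The gap of 36 is the assumed treatment effect itself.

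**Formula.** A share 7.2/24 = 0.30 of would-be cases is prevented. Let M be the mean score of all control cases and m the mean that the prevented cases would have had. If nothing changes in the remaining cases, the intervention-case mean is (M − 0.3m)/0.7.

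**Example.** The documents give no POEM means, so these are assumptions: half of control cases mild at 5, half worse at 12.2. Then M = (0.12 × 5 + 0.12 × 12.2)/0.24 = 2.064/0.24 = 8.6.

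| Cases prevented | m | Cases only: control vs intervention | All randomised, no AD = 0: control vs intervention |
|---|---|---|---|
| Only mild | 5 | 8.6 vs (8.6 − 1.5)/0.7 = 10.14 | 2.06 vs 0.048 × 5 + 0.12 × 12.2 = 1.70 |
| Unrelated to severity | 8.6 | 8.6 vs (8.6 − 2.58)/0.7 = 8.6 | 2.06 vs 0.168 × 8.6 = 1.44 |
| Only worse | 12.2 | 8.6 vs (8.6 − 3.66)/0.7 = 7.06 | 2.06 vs 0.12 × 5 + 0.048 × 12.2 = 1.19 |

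**Other assumed distributions.** Case scores follow a gamma distribution capped at 28, SD 6, with 120 against 84 cases and no change in remaining cases. The first two result columns compare intervention with control cases.

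| Assumed control-case mean | Prevention | Difference | Chance of significant apparent harm | Power, all randomised, 500 per arm |
|---|---|---|---|---|
| 8 | unrelated to severity | 0.00 | 2.5% | 59% |
| 8 | milder cases preferentially | +1.33 | 35% | 24% |
| 8 | mildest 30% | +2.37 | 85% | 9% |
| 10 | unrelated to severity | 0.00 | 2.5% | 66% |
| 10 | milder cases preferentially | +1.37 | 37% | 34% |
| 10 | mildest 30% | +2.51 | 91% | 15% |

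At mean 8, if the remaining cases truly improve by 10%, the last two patterns still give +0.40 and +1.34. A uniform downward shift in a latent liability works differently: children who are cases either way improve by 0.256 latent SD, but the cases-only comparison shows 0.057. That is attenuation, not reversal.

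**Power of the all-randomised POEM test in the example with only mild cases prevented.** Control variance is 0.12 × 25 + 0.12 × 148.84 − 2.064² = 16.60. Intervention variance is 0.048 × 25 + 0.12 × 148.84 − 1.704² = 16.16. SE = √((16.60 + 16.16)/500) = 0.256, z = 0.36/0.256 = 1.41, and power is Φ(1.41 − 1.96) ≈ 29%.

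**The case against.** The strongest reply has four parts.

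- **Severity is already covered without this selection.** CS1-AD and CS2-AD are cumulative-incidence endpoints in which a child without AD is a non-event. Topical treatment is tested in the ITT dataset as well as the AD dataset, and sleep days are summarised for ITT. This stands, and it limits the consequence. It does not make the POEM and IDQOL test interpretable.
- **Reversal is only one scenario.** A reader might infer that a real benefit will show up as harm. The documents do not support that. They say nothing about which cases emollient would prevent, and the same inputs also give no bias or an overstated benefit.
- **An all-randomised test has costs of its own.** Power is low, most scores are zero, and the result partly repeats the primary comparison. A zero IDQOL total would also conflict with planned data: SAP 5.1 item 11 takes sleep days from IDQOL item 4, and Table 4 summarises them for all children, so a child without AD can have a non-zero item. All of this stands, and it narrows the fix.
- **The stakes are secondary.** SAP 3.2 rests type I error on a single primary outcome, and the protocol deliberately measures these scores in cases. This is correct. It justifies describing severity among cases, but not a formal arm comparison at 0.05.

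**Conclusion.** The point holds in this form: the cases-only POEM and IDQOL difference does not estimate a treatment effect, and item 8 contradicts itself on the dataset. At the planning rates, and with the assumed POEM values of 5 and 12.2, the comparison runs from 8.6 against 10.14 to 8.6 against 7.06 with no remaining case altered. The direction depends on which cases are prevented, which the documents do not state, so neither a favourable nor an unfavourable result could be credited to the intervention.

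The case rates come from the SAP. The POEM means, spreads and prevention patterns are assumptions. Apparent harm is possible but not established as likely. The primary relative risk is unaffected.

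**What to change.** 1. Reconcile the heading of SAP 5.4 item 8 with sub-items 8a and 8b, in line with 5.1 item 9 and Table 4.
2. Report POEM and IDQOL means among cases as description, without a p-value or causal claim.
3. Make the between-arm severity test all-randomised. Either use an ordered outcome (no AD, mild, moderate, severe) built from the parent global severity already collected, or use POEM with children without AD scored 0 and the bootstrapped standard errors SAP 5.4 already allows. Read it alongside CS1-AD and CS2-AD.
4. Do not zero-score the IDQOL total.
5. Define no AD by the chart-based GS-AD outcome. The questionnaires are triggered by survey logic and the AD population by the chart, so the two can disagree and the rule must be written down. Handle missing AD status under section 5.9, not as 0.

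No new data are needed, but this is more than one recoded variable: the rules in step 5 have to be set before the data are locked. The statistical cost is many zeros, partial overlap with the primary comparison, and low power: about 29% in the example with only mild cases prevented, and 9% to 59% in the scenarios with an assumed case mean of 8.
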